Adverse events for MRI scans are very rare. Millions of MRI scans are performed in the US every year, and the FDA receives around 300 adverse event reports for MRI scanners and coils each year from manufacturers, distributors, user facilities, and patients. The majority of these reports describe heating and/or burns (thermal injuries). Second degree burns are the most commonly reported patient problem. Other reported problems include injuries from projectile events (objects being drawn toward the MRI scanner), crushed and pinched fingers from the patient table, patient falls, and hearing loss or a ringing in the ear (tinnitus). The FDA has also received reports concerning the inadequate display or quality of the MR images.³³

An MRI scan may reveal an abnormality that is already present in a subject's body, such as a cyst or tumor. Subjects will be advised that such a finding might require additional studies, and maybe even treatment, neither of which would be paid for by the investigators, the sponsor, or UM.

2.3.5 **Quantitative Sensory Testing (QST)**

For both TMD subjects and healthy volunteers, quantitative sensory testing will be performed (thermal and algometry) in four areas: right and left superficial masseter muscle, and dorsum of the hands. This stimulus, though it may feel mildly painful, does not produce any skin damage.

Thermal stimulation

We will use a standard clinical evaluation program designed for the Pathway system (MEDOC-Israel). This program is comprised of a series of hot and cold stimuli that are delivered from a baseline temperature of 32°C, bilaterally. The subject will control the heating/cooling unit with a computer mouse. They will be instructed to tap the mouse button at the first perception of pain. Each stimulus (hot and cold) will be delivered three times in each location, and the Pathway program records the average temperature.

Algometry

We will use an algometer (Somedic, Sweden) to define pressure pain threshold and tolerance in the four regions bilaterally, and in a randomized fashion. Each area will be

evaluated three times, and the ultimate pressure pain threshold and tolerance levels will be the average of the three measurements recorded. For the evaluation of motor function, we will perform the exam according to the Research Diagnostic Criteria (RDC) guidelines and forms (e.g., range of motion). The QST is not associated with pain lasting beyond the study period or any irreversible damage to the body.

2.3.6 *Collection of Blood Samples for Biomarkers and/or Genetic Analysis*

Serial biomarker blood draws and a blood sample for genetic testing will be collected for this study. Serial blood samples that do not exceed a total of 45mL (3 Tbsp) will be collected during the PET scan for biomarker analysis. This blood will be collected from a separate intravenous line placed into the vein of the arm that is opposite the arm used for the tracer injection. One additional, individual collection for genetic analysis will be performed for future studies. The blood for genetic analysis will be collected prior to tracer administration and will not exceed 25 mL (2.4 Tbsp) per scan. No more than 70 mL of blood will be collected per subject per day; therefore, a total of 140 mL blood will be collected, per subject, for following the study per protocol. These samples will be stored for potential analyses after the study. This procedure carries with it the expected risks associated with a blood draw, particularly the chance of mild bruising and pain. Trained personnel will perform blood collection using standard procedures to reduce the risks. No repeated phlebotomy is planned. If the second IV stops working or cannot be started, the scan will be canceled. Movement during data capture is not tolerable.

2.3.7 *Administration of Pregnancy (Urine Dipstick) & Drug Screening Tests*

Pregnancy tests (urine dipstick) will be asked of female participants to assure that they are not pregnant prior to each PET scan. The results are immediately recorded in the research record (only) and are shared with the subject.

The multi-drug screening test employed is also a dipstick and uses monoclonal antibodies to selectively detect specific drugs and drug metabolites in urine. If a positive result is obtained, a repeat test may be performed on a second sample.

There is a risk of loss of confidentiality and/or feeling uncomfortable about sensitive information such as drug use status. Such information could be inadvertently and inappropriately shared with third parties. These risks will be minimized by coding the data. Additionally, the results for the drug screen will be recorded in the research record (not in the clinical record) and shared only with the subject.

2.3.8 *Administration of Questionnaires*

Subjects will be asked to complete several questionnaires at each visit. Although each questionnaire is not stressful when answered alone, completing multiple surveys in a row may lead to a low level of mental fatigue.

2.3.9 *Collection of Medical/Dental History*

At the initial Screening visit (after completion of a written informed consent process) a review of the subject's medical/dental history, with emphasis on TMD pain will be performed by the Investigators. This will include a review and evaluation of the inclusion and exclusion criteria, and the determination of eligibility for the subject.

Research records will be kept in a separate research file that does not include names, registration numbers, or other information that is likely to allow someone other than the researchers to link the information to the subject. Subject data will be coded. Research records will be kept confidential to the extent provided by federal, state and local law. Subjects will not be identified in any reports on this study; however, the National Institutes of Health, the United States Food and Drug Administration, and the institutional review board monitoring this study may inspect the records of this investigation.

Genetic research may provide information about who is at risk to develop a disease. Some people may find this information stressful or uncomfortable. While our research is focused primarily on pain mechanisms through new genetic technologies that allow us to look at all of the information across the genome, we may learn information about subjects regarding diseases not related to pain. We do not intend to release the results of the genetic testing to subjects.

If multiple members of a family are enrolled in research, information from this research may identify previously undisclosed biological relationships (i.e. non-paternity or non-maternity). There is an unlikely but possible risk of a breach of confidentiality. To reduce this risk, the databases developed for this project will not contain information that is traditionally used to identify subjects, such as name, address, telephone number, or social security number. It is also possible that there could be violations to the security of the computer systems used to store the codes linking genetic and medical information to subjects. These codes will be maintained only at UM.

2.3.10 *Conclusion*

After careful consideration of all the neuroimaging, neuromodulatory, and associated methods outlined above, which our lab has applied and published on for several years, we firmly believe that this study is of non-significant risk to the patients. It has the capacity to provide vital information to increase our understanding of the central mechanisms of TMD pathophysiology as well as lead to potential new treatments for those patients where currently available treatments have failed.

2.3.11 *Potential Benefits*

There is no direct benefit to the participants in this project. Subjects will be informed that the medical significance of these studies is presently unknown and that the results will not influence their subsequent medical care. However, these studies may help to

determine the molecular mechanisms to suppress pain in subjects suffering from TMD via the μ -opioid system.

3 OBJECTIVES

3.1 Study Objectives

3.1.1 *Primary Objective*

The primary effectiveness objective is to investigate whether 10 daily sessions of primary motor cortex (M1) HD-tDCS will result in a significant reduction in clinical pain intensity at rest in chronic TMD subjects 4 weeks after completion of HD-tDCS sessions, as measured by a visual analog scale (VAS) pain score.

3.1.2 *Secondary Objectives*

The secondary objectives are as follows:

- To investigate whether 10 daily sessions of M1 HD-tDCS will result in significant reductions in clinical pain intensity (at rest) and experimental (sustained masseteric pain stress challenge) measures in chronic TMD subjects at 1 week after completion of HD-tDCS sessions, as measured by VAS pain score assessments, obtained during the baseline PET (#1) session and follow-up PET (#2) session.
- To investigate whether 10 daily sessions of M1 HD-tDCS will result in significant short-term and/or long-term changes in clinical pain intensity and area measures in chronic TMD subjects treated with HD-tDCS compared to those who receive sham treatment, as measured by GeoPain measures.
- To investigate whether repetitive active M1 modulation induces increase of μ -opioid receptor (μ OR) non-displaceable binding potential (BP_{ND}) in the thalamus and other pain-related regions in the brains of chronic TMD subjects from the baseline PET (#1) session to the follow-up PET (#2) session, 1 week after completion of HD-tDCS sessions.
- To investigate whether any μ OR BP_{ND} changes from baseline PET (#1) session to follow-up PET (#2) session are associated with changes in mean clinical and experimental pain measures, as measured by VAS pain scores in chronic TMD subjects who receive HD-tDCS treatment compared to those subjects who receive sham treatment.
- To investigate whether chronic TMD is associated with μ OR BP_{ND} changes as compared to healthy subjects during baseline PET (#1) session at rest, and during experimental sustained masseteric pain stress challenge.

3.2 Study Outcome Measures

3.2.1 *Primary*

The primary effectiveness endpoint will be as follows:

Change in clinical VAS pain score from baseline (Screening Day) to 4 weeks after completion of HD-tDCS sessions (Follow Up #2).

3.2.2 *Secondary*

The secondary effectiveness endpoints will include the following:

- Change in clinical VAS pain score at rest and during sustained masseteric pain stress challenge from baseline PET (#1) session to follow-up PET (#2) session, 1 week after completion of HD-tDCS sessions.
- Short- and long-term changes in GeoPain measures (pain area, intensity, and their summation) from baseline daily over the treatment period and through follow-up (1, 4, and 8 weeks after completion of HD-tDCS sessions).
- Change in μ OR BP_{ND} levels and clinical VAS pain score from baseline PET (#1) session to follow-up PET (#2) session, 1 week after completion of HD-tDCS sessions.
- Change in μ OR BP_{ND} levels at rest and during experimental sustained masseteric pain stress challenge during PET (#1) in chronic TMD patients as compared to healthy subjects.

3.2.3 *Safety*

All adverse events (AEs) will be solicited via generalized questioning at each study visit, beginning after informed consent.

In addition, questionnaires for PET Screening and HD-tDCS AEs will solicit information about the following symptoms/side effects of specific interest for HD-tDCS: headache, neck pain, scalp pain, scalp burns, tingling, skin redness, sleepiness, trouble concentrating, acute mood changes, and “other (specify).” These AEs were chosen because comprehensive reviews and a consensus article regarded them as common^{34,35}.

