5 STUDY ENROLLMENT AND WITHDRAWAL

5.1 Subject Inclusion Criteria

To be eligible to participate in this study, an individual must meet all of the following criteria:

- Provide signed and dated informed consent form;
- Male or female, aged 18 to 65 (inclusive);
- tDCS naïve; and
- Willing to comply with all study procedures and be available for the duration of the study.

In addition, **TMD subjects** must qualify as:

- Diagnosed with chronic TMD as defined by the Diagnostic Criteria (DC) for TMD and the American Academy of Orofacial Pain (DC/TMD)³⁶:
“Chronic TMD pain and dysfunction for at least one year from the clinical exam session (DC/TMD: Masticatory myofacial pain with/without referral) not adequately controlled by previous therapies (eg, NSAIDs, muscle relaxants)”
- TMJ open-surgery naïve;
- TMD maximum pain score pain of greater than or equal to 3 (moderate to severe) on a 0-10 VAS, despite existing treatment, for 3 days in the 7 days preceding study consent, based on report at the screening session;
- If taking pain medications, the dose regimen must be stable for at least 4 weeks prior to screening; and
- Willing to halt the introduction of new medications for chronic TMD symptoms during the study.

Emphasis is therefore placed on generalizability and chronicity of symptoms.

OR

To qualify as a **Healthy Volunteer**, subjects must be:

- Without self-reported history of systemic disorders or other chronic pain disorders, including migraine.

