5.2 Subject Exclusion Criteria

An individual who meets any of the following criteria will be excluded from participation in this study:

- Existence of chronic pain disorder(s) other than TMD
- VAS rating lower than 3 during Screening Visit (week -3)
- History of a traumatic brain injury
- History or current evidence of a psychotic disorder (e.g. schizophrenia) or substance abuse (self-reported)
- Bipolar or severe major depression, as evidenced by a Beck Depression Inventory³⁷ score of ≥ 30
- Ongoing, unresolved disability litigation (self-reported)
- History of neurological disorder (e.g. epilepsy, stroke, neuropathy, neuropathic pain; self-reported)
- Opioid pain medications taken within the past 3 months
- Past allergic response to opioids or chemically related drugs (e.g., carfentanil)
- Excluded by MRI Center or PET Center safety screening checklist (as administered by study staff)
- Drug test positive for opioid or recreational drug (e.g., cannabis) at the time of the PET scan visits
- Pregnant or lactating (negative urine pregnancy test must be available before any PET procedures are initiated)
- Treatment with an investigational drug, device or other intervention within 30 days of study enrollment
- Anything that would place the individual at increased risk or preclude the individual's full compliance with or completion of the study (e.g., medical condition, laboratory finding, physical exam finding, logistical complication).

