7.2 TMD Patients

Prescreening (Study Week -8)

Chronic TMD subjects interested in the study will be prescreened via a phone interview using an IRB-approved checklist.

Screening
(*Study Week -3*)

The activities assigned to the Screening Visit will be completed within 3 weeks prior to the first session of Week 1. Following the informed consent process, subjects will undergo a baseline assessment and the completion of questionnaires, as listed in the study schedule (Table 2). The baseline visit will include a medical/dental history with limited physical that involves clinician assessed DC/TMD (Diagnostic Criteria/Temporomandibular Disorder) status. Also covered are a comprehensive medication history (6 months) and a review of eligibility.

Baseline PET/MRI
(*Study Week -1*)

Within 7 days preceding randomization and the first study treatment, subjects will undergo an MRI, as well as a PET scan that uses an [¹¹C]carfentanil radioligand, with a masseter muscle pain challenge via a 5% hypertonic saline intramuscular infusion. Pain questionnaires will also be completed during this visit window. All procedures are targeted for the week prior to HD-tDCS; however, due to occasional scheduling difficulties, they may be completed within 14 days prior to Day 1 of HD-tDCS. Completion of all procedures may require more than one clinic visit.

Treatment HD-tDCS
(*Study Weeks 1 through 2*)

Beginning at Day 1 of HD-tDCS, subjects will be randomized to active treatment or sham procedure. They will then attend 10 sessions, 1 each weekday (Monday through Friday) over a 2-week period, and will receive either the M1 HD-tDCS treatment or the sham treatment, preceded and followed by questionnaires. Missed days can be doubled and/or rescheduled within the 2-week schedule, as necessary, with study team approval.

Follow-up PET
Follow-up MRI &
First Follow-up Visit
(*Study Week 3*)

Within 7 days following the last study treatment, subjects will undergo an MRI as well as a PET scan that uses an [¹¹C]carfentanil radioligand with a masseter muscle pain challenge via a 5% hypertonic saline intramuscular infusion. Pain questionnaires will also be completed during this visit window. All procedures are targeted for the week following completion of HD-tDCS; however, due to occasional scheduling difficulties, they may be completed within 14 days following Day 10 of HD-tDCS. Completion of all procedures may require more than one clinic visit.

Follow-Up #2 & #3
(Study Weeks 6 and 10)

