Brief Pain Inventory (BPI; Short)		X			X	X	X	
Pittsburgh Sleep Quality Index		X ⁷			X	X	X	
PET Subject Information Sheet			X ⁷		X			
tDCS Effects Questionnaire				X	X	X	X	
HD-tDCS Sham/Placebo Assessment				X				
DC for TMD Symptom Questionnaire		X ⁷			X	X	X	

¹ Target dates for PET/MRI are during the week prior to Day 1 HD-tDCS session (Baseline) and during the week after completion of HD-tDCS sessions (Follow-up); an additional week window is allowed to account for scheduling issues. The "Magnetic Resonance (MR) Safety Screening Form" is completed prior to each MRI scan. See Section 2.3.4.

² Procedures may require more than one clinic visit.

³ Applicable if subject completes an in-person visit.

⁴ If subject is deemed eligible, schedule subject visits and provide subject with instructions for PET & MRI.

⁵ Missed days can be doubled in the (M-F) x 2 schedule, with study team approval. See Section 7.

⁶ These assessments will be conducted at Screening, before and after MRI/PET and tDCS Sessions, and at Follow-up visits.

⁷ Questionnaires to be completed by healthy volunteer subjects at the timepoints indicated.

⁸ HD-tDS sessions will be scheduled M-F. See Section 7.2.

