7.4 Repeated Screening Visit

If a subject completes a Screening Visit (ie, signs informed consent), but does not complete a Randomization Visit (first session of HD-tDCS Week 1) within 3 weeks, the subject may continue participation by repeating a limited to full Screening visit.

Informed consent must be re-obtained if there have been changes to the informed consent document since the version that was originally signed. These changes might include:

- New “reasonably foreseeable” risks or side effects judged to be “definitely related” to the research.
- Changes are made to the protocol such as additional tests or research procedures that may affect subjects’ willingness to participate, rights, welfare, or safety.
- New information included that may affect subjects’ willingness to participate.
- A change in principal investigator and contact information.

The remaining Screening evaluations and questionnaires to be repeated are to be determined based on clinical relevance by the PI.

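### The primary change score rests on one Screening VAS that apparently also gates entry: no bias between arms, but an untreated fall within each arm and pre-treatment readings left unused

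*Combined protocol and SAP*

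**What the plan says.** - **Primary endpoint (3.2.1):** "Change in clinical VAS pain score from baseline (Screening Day) to 4 weeks after completion of HD-tDCS sessions (Follow Up #2".
- **Entry rule (5.2), exclusion:** "VAS rating lower than 3 during Screening Visit (week -3". Section 5.1 adds a recalled criterion: maximum pain of at least 3 "for 3 days in the 7 days preceding study consent, based on report at the screening session".
- **Timing (7.2):** "The activities assigned to the Screening Visit will be completed within 3 weeks prior to the first session of Week 1".
- **Late patients (7.4):** if the 3 weeks pass, "the subject may continue participation by repeating a limited to full Screening visit". On what is repeated: "The remaining Screening evaluations and questionnaires to be repeated are to be determined based on clinical relevance by the PI". No rule says which Screening VAS is then the baseline.
- **Other VAS readings (Table 2, questionnaires, footnote 6):** "These assessments will be conducted at Screening, before and after MRI/PET and tDCS Sessions, and at Follow-up visits". The PET/MRI #1 procedures are targeted for the week before treatment, but "they may be completed within 14 days prior to Day 1 of HD-tDCS". No entry rule uses these later VAS readings.
- **1-week VAS endpoint (3.2.2):** change from the PET #1 session to the PET #2 session, so clinical VAS has two reference points in the trial.
- **Primary model (12.3.2.1):** change from baseline with group, time and their interaction. No baseline covariate is listed. Section 12.4 leaves the final detail to a separate SAP.

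**The concern.** A patient whose pain happens to be high at Screening is more likely to pass the cut-off than one whose pain happens to be low. If the reading that passes the cut-off is also the reference for improvement, pain will on average appear to fall by week 6 without any treatment effect.

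Two things are at stake.

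- **Within-arm interpretation.** Hypothesis 1 (12.1.1) compares active with sham. The primary objective (3.1.1) speaks only of a reduction and names no comparator, and the model in 12.3.2.1 is described in terms of change after active treatment. A built-in fall would inflate any within-arm reading of that reduction, and the apparent sham response with it.
- **Precision.** A trial planned around 24 evaluable patients per arm would use one early reading, unadjusted, while readings closer to treatment stay out of the primary analysis.

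**Working it through.** **The plan's own figure.** Section 12.2 gives 24 per group for 80% power at an effect size of 1.2 (two-group t-test, two-sided 0.05), and 24/0.8 = 30 with dropout. If 1.2 is a standardized effect, 12 per group suffice and 24 give 98% power. The figure of 24 fits a standardized effect of 0.83, that is, 1.2 VAS points with an SD of 1.2/0.83 ≈ 1.45. The text does not say which is meant.

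**Assumptions.** The documents give no VAS SD or repeat correlation. I take the unselected resting VAS as normal with mean μ = 4 to 5 and SD σ = 1.5 to 2.0, equal correlation r = 0.5 to 0.7 between all occasions, and entry at Screening VAS ≥ 3. Let a = (3 − μ)/σ, λ = φ(a)/[1 − Φ(a)] and V = 1 + aλ − λ² (the variance ratio of the selected Screening reading).

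**Untreated fall from Screening** = (1 − r)σλ.
- Largest (μ 4, σ 2, r 0.5): a = −0.5, λ = 0.509; 0.5 × 2 × 0.509 = 0.51 points.
- Smallest (μ 5, σ 1.5, r 0.7): a = −1.33, λ = 0.180; 0.3 × 1.5 × 0.180 = 0.08 points.
- From readings not used for selection, the fall is 0 in this model.

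**Effect on the comparison.** In a simulation with a true difference of −1.2, the sham change was −0.51 from Screening and −0.01 from a later reading. The active-minus-sham difference was −1.21 and −1.20. Both arms shift and the contrast does not.

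**Variance, in units of σ².**
- Change from Screening: V(1 − r)² + 1 − r²
- Change from one later reading: 2(1 − r)
- Change from the mean of two later readings: 1.5(1 − r)
- Mean of two as covariate, with k = r²(1 − V): (1 − k) − (r − k)²/[(1 + r)/2 − k]

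| Setting | Screening | One later | Mean of two | Mean of two, covariate |
|---|---|---|---|---|
| μ 4, σ 2, r 0.5 (V 0.486) | 0.872 | 1.000 | 0.750 | 0.649 |
| μ 5, σ 1.5, r 0.7 (V 0.727) | 0.575 | 0.600 | 0.450 | 0.419 |
| μ 5, σ 1.5, r 0.5 (V 0.727) | 0.932 | 1.000 | 0.750 | 0.658 |

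Over the whole range, checked by simulation with scores clipped to 0–10, the variance relative to the planned change score is:
- mean of two, plain change: 14% to 22% lower;
- mean of two, covariate: about 26% to 29% lower;
- Screening VAS kept but used as a covariate: 8% to 19% lower;
- one later reading, plain change: 4% to 15% **higher**;
- one later reading, covariate: 13% to 21% lower.

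A single later reading does badly as a plain change because selection narrows the spread of the Screening reading. If correlation decays with time instead, a single later reading may be slightly better or slightly worse than Screening as a plain change.

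**Power.** Set the planned analysis at 80% with 24 per arm (standardized effect 0.83). Residual variance ratios of 0.74 and 0.71 raise the effect to 0.83/√0.74 = 0.96 and 0.83/√0.71 = 0.98, which give about 90% and 91%.

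**The case against.** **The comparison is randomized against sham, so selection on Screening cannot bias it.** This stands. A reader might infer from the selected baseline that the primary result is compromised. Hypothesis 1 is a between-arm contrast, and the simulation shows it unchanged.

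**The noise does not come from the selection.** This also stands. It is tempting to say that the gated reading itself makes the change score noisier, but the table shows that swapping in one later reading usually makes it worse. The gain comes from averaging and from covariate adjustment. Part of it is available by adjusting for the Screening VAS alone.

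**The gate may not act on the endpoint reading.** Section 5.2 does not say that its VAS is pain at rest, and section 5.1 uses recalled maximum pain. If 5.2 merely enforces the recalled rule, resting VAS is not cut at 3 and the computed fall does not apply as it stands. Requiring pain on 3 of 7 days also means that one bad day is not enough for entry. Table 2 lists one VAS instrument at Screening, which makes the link likely but not certain. The case for averaging and adjusting does not depend on it.

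**Two further inferences fail.** A reader might conclude that the 1-week and 4-week VAS results cannot be placed on one time course. They can, because VAS is scheduled at Screening, PET/MRI #1, the sessions and every follow-up. Nor would a new baseline give more room to improve to patients already below 3 on Day 1 (5% to 21% under the same assumptions); it would only stop their earlier drop being counted as response.

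**The separate SAP may already adjust for baseline.** That cannot be excluded, but 3.2.1 fixes the Screening reading as the reference and 12.3.2.1 lists no covariate.

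**Conclusion.** The point holds as one of interpretation and efficiency, not of validity. The planned baseline is a single reading, up to 3 weeks old, that apparently also decides entry. It leaves the active-versus-sham difference unbiased. It builds in an untreated fall of about 0.1 to 0.5 VAS points per arm, which matters for any within-arm statement and for the apparent sham response.

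Using the mean of the two later readings as a covariate would cut residual variance by about 26% to 29% relative to the unadjusted change from Screening. That takes 80% power to about 90% if the plan's 1.2 means VAS points with an SD near 1.45. If 1.2 is standardized, power is already about 98% and little is gained.

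These sizes rest on the assumed mean, SD and equal correlations, and the fall also rests on the inferred gate. The lack of a rule for repeat screening under 7.4 is a plain gap that needs no assumption.

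**What to change.** 1. In 3.2.1 and 12.3.2.1, define baseline for the 4-week comparison as the mean of two VAS-at-rest readings already scheduled: before PET/MRI #1 (before the saline infusion) and before HD-tDCS session 1 (before both randomization and stimulation). State that order for Day 1, because 7.2 places randomization on that day without saying when VAS is taken.
2. Include this baseline as a covariate in the primary model. Screening VAS may be added as a further covariate rather than discarded.
3. If only one of the two readings is available, use it only with covariate adjustment, not as a plain change score.
4. Keep PET #1 to PET #2 for the 1-week VAS endpoint, so that it stays paired with the same-session BPND change (3.2.2, Hypothesis 5).
5. Report the Screening-based change as a sensitivity analysis.
6. In 7.4, state which Screening VAS counts after a repeat visit. In 5.2, state whether the VAS used for exclusion is the at-rest reading.

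**Cost:** wording in the protocol and SAP and a fixed order of events on Day 1; no new visit or questionnaire. The within-arm fall from baseline will look smaller, and the gain in power may be slight, depending on what 1.2 means.
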